Our overriding hypothesis is that radiation interacts, enhances, and potentially accelerates the individual patient's genetic predisposition to develop breast cancer, but does not fundamentally alter the molecular phenotype. To test this hypothesis, we plan to obtain the 54 (or more if available) formalin-fixed, paraffin-embedded tissue samples of the secondary breast cancer cases from the CCSS bio-repository from women who received thoracic radiation. We plan to subject these samples to RNA extraction, using established protocols that yield expression profiles that are highly concordant with frozen tissue.¹²⁻¹³ This mRNA will then be assayed for quality and quantity and amplified accordingly.¹⁴ The resultant cDNA will then be hybridized, at our core facility, using the Affymetrix U133A gene chip. Using the GeneSpring software platform, gene expression data will then be analyzed using supervised methods (which will query the expression levels of specific, hallmark genes that define the molecular subtypes of breast cancer) as well as unsupervised methods (within the set of 54 cases as well as in conjunction with 1,619 general population cases) to determine the prevalence of known, and potentially novel, molecular subclasses of these secondary tumors. Once the subclass designation is established for the 54 secondary breast cancers, the patient demographics and overall survival time after diagnoses will be compared to their spontaneous/general population

counterparts. Generating this working data will enable us to answer the following clinically important questions, which represent our specific aims:

- Specific Aim 1: What is the prevalence/distribution of Luminal A, Luminal B, Basal, Her2-enriched and breast-like breast cancer subtypes among those women who received thoracic radiation during childhood for their pediatric malignancy versus that observed in the general population of spontaneous breast cancers? Consistent with our overriding hypothesis is that the prevalence of these molecular subtypes will approximate that observed in the general, spontaneous breast cancer population. Therefore, assuming radiation induced breast cancers are representative of the general population, approximately 50% will be Luminal A, 20% will be Luminal B, 20% will be Basal, and 10% will be Her 2+.

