- 2. Specific Aim 2: Is there a clinical outcome difference in terms of overall survival after diagnosis within the molecular subclasses of the 54 cases of secondary breast cancers from the childhood cancer survivors and compared to spontaneous breast cancers from the general population cases with the same molecular subclass? We believe the answer to this question will determine if radiation has an independent role in expediting the development of various breast cancers and/or augmenting the biologic lethality of the disease.

If our overriding hypothesis is incorrect, then 2 other potential phenomena may be identified with this data:

- 1. Radiation to the chest during childhood induces a specific type of one of the established molecular subclasses of breast cancer, which may or may not have the same virulence as seen in the general breast cancer population.
- 2. A novel molecular subclass(es), unique to patients with radiation to the chest during childhood, is elucidated. If so, multiple questions can be answered using this data:
 - i. What are the hallmark genes that define this group?
 - ii. What are the patient demographics at time of onset? And
 - iii. What is the expected survival time within this group(s)?

Analysis framework:

Outcome of interest

Primary endpoint:

- The patterns of gene expression and distribution of molecular subtypes of radiation induced breast cancer compared to spontaneous/primary breast cancer

Secondary endpoints:

- Overall survival: Time from diagnosis of breast cancer to death of any cause
- Patient demographics at the time of breast cancer diagnosis.

Subject population:

Inclusion criteria

- 1. Cases: Survivors from the Childhood Cancer Survivor Study Cohort who subsequently developed breast cancer after thoracic radiation, with available breast tissue
- 2. Controls: 1,619 patients with spontaneous primary breast cancers, without previous cancer diagnosis or treatment, obtained from previously published research studies for which the gene expression data is publically available, will comprise the general, spontaneous breast cancer population. The previously published gene expression data is analyzed for subtype composition and is presented in **Figure 2**.¹⁵⁻²²
 - a. All ages
 - b. All stages
 - c. Tumor sample obtained from biopsy or surgical specimen prior to any non-surgical therapy
 - d. Biopsy proven invasive ductal, lobular, mucinous, tubular, colloid or papillary (i.e. epithelial) carcinoma of the breast

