The first layer of analysis will consist of determining the distribution of the molecular subtypes of the secondary breast cancers. The RNA will be isolated from the study samples and in a manner similar to the clustering analysis of the control population, the gene expression status of the 249 genes that define the molecular subclasses will be performed in an unsupervised manner on the 54 study and 1,619 control cases together. To account for batch-effect and paraffin extraction, log-transformation and normalization using the RMA method will be performed, again using GeneSpring software, with all cases included. Genes will undergo an independent QA process (to determine if there is signal susceptibility to the formalin fixation and parafinization process) and will be excluded from the final clustering analysis. The placement of the study cases within the cluster groups, as defined predominantly by the control population, will determine the subclass assignment. A chi-square test will be used to compare the distribution of molecular subtypes between the primary and secondary breast cancers.

The raw data from the .cel files of the study population will also be compared. This will be especially important in the event of the formation of a separate clustering group by the radiation-induced cases and a novel subtype is identified. From this analysis, the genes that define this new subclass will be identified and reported. This approach will also allow the identification of gene expression, unique to previously radiated breast tissue, which spans across all subtypes.

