Figure 1: Molecular subtypes of breast cancer identified. Gene expression profiles of primary breast cancers demonstrating 5 distinct molecular subtypes: luminal A, luminal B, Basal, ERBB2+ (HER2 enriched [ERBB2+]), and normal breast-like. From Perou CM et al. Molecular portraits of human breast tumours. Nature 2000;406:747-52.

Figure 2: Our preliminary data. Supervised clustering analysis using 249 genes identified as hallmark genes in determining the established molecular subtypes applied to 1,619 cases from publicly available U133A-derived .cel files,¹⁵⁻²² after log-transformation and normalization using the RMA method. The approximate subclass designation is noted (scaling precludes detailed dendrogram). Collectively, these cases reflect an adequate, heterogeneous control population. Data obtained from radiation-induced breast cancers will be analyzed within the context of this general population of spontaneous breast cancers.

Special considerations:

The principle investigator has significant experience in extracting RNA and DNA from paraffin-embedded tissues for global profiling analyses.²³⁻²⁵

References:

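### Radiation history is aliased with laboratory in the case-control expression comparison, RMA cannot separate them, and a case-only cluster or cross-subtype signature therefore cannot be attributed to radiation

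*Protocol*

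**What the plan says.** The protocol's specific aims describe the case material as "formalin-fixed, paraffin-embedded tissue samples of the secondary breast cancer cases from the CCSS bio-repository". After RNA extraction and amplification, "The resultant cDNA will then be hybridized, at our core facility, using the Affymetrix U133A gene chip". Under Subject population, the 1,619 controls had no earlier cancer or treatment and were "obtained from previously published research studies for which the gene expression data is publically available"; the Figure 2 caption describes the preliminary clustering as "applied to 1,619 cases from publicly available U133A-derived .cel files", citing references 15 to 22.

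The first layer of the Statistical and Analytic Plans clusters cases and controls jointly on 249 genes, and a case's position among the resulting clusters decides its subtype. For technical differences the section states: "To account for batch-effect and paraffin extraction, log-transformation and normalization using the RMA method will be performed". It adds a gene QA for sensitivity to fixation and embedding, with exclusion from the final clustering.

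The next paragraph compares the study population's raw array files. It calls this especially important "in the event of the formation of a separate clustering group by the radiation-induced cases and a novel subtype is identified", with the defining genes then reported, and says the approach will also allow "identification of gene expression, unique to previously radiated breast tissue, which spans across all subtypes".

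The specific aims plan "unsupervised methods (within the set of 54 cases as well as in conjunction with 1,619 general population cases"). The primary endpoint has two parts: expression patterns and subtype distribution, each compared with spontaneous breast cancer.

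**The concern.** No unirradiated tumour is processed with the cases, and no irradiated tumour comes from a control laboratory. Any gene whose signal is altered by the core's amplification, hybridisation or run, or by paraffin storage, will differ between cases and controls in every subtype. That is the pattern the plan would read as specific to irradiated tissue. If such shifts are large enough, they could also pull the cases into a cluster of their own, which the plan's wording links to a novel subtype.

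The expression half of the primary endpoint and both alternative findings (a novel subclass and a radiation signature) thus rest on a contrast that processing alone can produce. The protocol's only stated answer to batch is a normalisation step that cannot do this job.

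**Working it through.** **1. Identifiability.** For each gene, write expression as subtype mean + β·R + π·P + λ·L + error, where R = irradiated, P = paraffin and L = processed at the study core.

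- Cases (54): R = P = L = 1.
- Controls (1,619): R = L = 0. P = 0 if the control tissue was not paraffin, which the protocol implies but does not state.

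The design matrix [1, R, P, L] over 54 + 1,619 = 1,673 samples has rank 2 of 4, so only the sum β + π + λ can be estimated. If some controls were in fact paraffin, P would separate from R, but R and L would remain the same column and β would still not be estimable. The problem with laboratory therefore does not depend on how the controls were preserved.

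**2. What RMA leaves behind.** The protocol gives no figure to reproduce, so this step is a simulation on assumed inputs. It used 5,000 genes, 249 of them subtype genes; within-subtype SD 0.7 log2; the protocol's expected mix of 50/20/20/10%; and **no radiation effect**. All 54 cases received a gene-specific shift with mean -0.5 log2 and the SD shown (no shift in the first row). Joint quantile normalisation (RMA's between-array step) followed, then average-linkage correlation clustering cut at 5 clusters, and Bonferroni-corrected t-tests on the non-subtype genes. There were three runs per setting, so the values are illustrative.

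| Shift SD, log2 | Shift SD ÷ 0.7 | Gene-specific shift remaining | Non-subtype genes falsely significant | Cluster holding most cases: share of all cases | Same cluster: proportion that are cases |
|---|---|---|---|---|---|
| 0 | 0 | n/a | 0% | 51% | 3% |
| 0.25 | 0.36 | 99% | 11% | 53% | 3% |
| 0.5 | 0.71 | 98% | 39% | 48% | 3% |
| 1.0 | 1.43 | 91% | 64% | 53% | 100% |
| 1.5 | 2.14 | 82% | 74% | 100% | 100% |
| 2.0 | 2.86 | 74% | 79% | 100% | 100% |

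Cases make up 54/1,673 = 3.2% of the pool, so 3% in the last column means they are mixed normally among the controls.

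**3. A second simulation.** This one used 249 genes, 800 controls, 12 replicates, shifts in within-subtype SD units, and two assumed degrees of subtype separation. It put 0% of cases in case-dominated clusters at a shift SD of 0.25 or less, 49 to 100% at 1.0, and 100% at 1.5.

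**4. Effect of the gene QA.** An idealised QA, which knows the true shifts, dropped the worst genes of the 249.

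- At 1.0 log2, dropping half removed the false cluster (case proportion back to 3%). Dropping a quarter did so only in part (36% on average over three runs).
- At 2.0 log2, a pure case cluster with about 73% of cases remained even after dropping half.
- The false signature genes were unchanged, at about 65% and 79%, because clustering QA does not touch that comparison.

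**5. Subtype assignment.** Assigning cases to the nearest control centroid misassigned 0% at every shift in the first simulation. In the second it was 100% correct at 1.0 and 94 to 100% at 1.5. The protocol uses position in the joint clusters instead, so these results support an alternative method and do not validate the planned one.

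**6. What would restore the contrast.** Adding unirradiated paraffin tumours processed at the same core (54 as an illustration) gives [1, R, paraffin/laboratory] rank 3 of 3, and β becomes estimable.

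**The case against.** The strongest reply is that the protocol has more protection than RMA. The gene QA addresses fixation, and step 4 shows that a good version can remove a false cluster at a moderate shift. That stands, and it would be wrong to infer that RMA is the sole safeguard. But the QA does not target laboratory, amplification or run, and it is not stated for the signature comparison.

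Four further inferences are tempting and go beyond the documents:

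- *The plan will report an artefact as a new subtype.* Neither simulation produced a case cluster at small shifts, the real shift is unknown, the protocol names no linkage method, and its wording is loose rather than a fixed rule that any separate cluster is a subtype. What is supported is that it could report one and could not tell the difference.
- *The subtype chi-square is shown to be distorted.* It is not. The demonstrated route is cases leaving the control clusters under joint placement.
- *The within-case clustering has been dropped.* The specific aims still plan it. The analysis section does not repeat it, which is not removal.
- *Confounding with paraffin is a stated fact.* The protocol never says how control tissue was preserved. The reference to concordance with frozen tissue and the stated need to account for paraffin make it a strong inference only.

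It might also be said that the raw-file comparison is meant within cases only. It would then contain no unirradiated tissue and could not show that anything is unique to irradiated tissue.

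**Conclusion.** The concern holds for two readings. Expression called specific to irradiated tissue across all subtypes cannot be separated from laboratory processing. This follows from the design alone, and even a small assumed shift (SD 0.25 log2) gave 11% false genes. A case-only cluster in the joint analysis could be an artefact: none appeared at 0.5 log2 or below, and about half or more of the cases were in one at 1.0 log2 or above before QA. The plan has no means of distinguishing the two explanations. The statement that RMA accounts for batch and paraffin is incorrect.

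The subtype distribution is affected mainly if cases leave the control clusters. Aliasing with laboratory rests on the protocol's text; aliasing with paraffin is inferred. The simulated sizes depend on assumed shifts, clustering method and subtype separation.

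**What to change.** 1. Delete the statement that log-transformation and RMA account for batch and paraffin. Define subtypes on the controls alone and assign each case by rank correlation to the control centroids, using QA-passing genes. Do not centre the cases separately, since that would pull their mix towards the controls'.
2. State that any case-only cluster in the joint analysis, and any case-control expression difference spanning all subtypes, will be reported as not separable from laboratory and paraffin processing, and not attributed to radiation without independent validation.
3. Apply the gene QA to the signature comparison as well.
4. Carry the within-54 clustering from the specific aims into the analysis section as the check for a new group, noting that it cannot by itself show that the group is unique to irradiated patients.
5. Optionally add an exploratory within-case trend of expression on chest radiation dose (already requested under Materials/Data needed from the CCSS, item 2.c.ii). State its limited power and possible confounding by childhood diagnosis and age at radiation.

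The cost is wording and some bioinformatics work, with no new samples. The overall case-control expression contrast is given up as evidence of a radiation effect, and items 4 and 5 do not restore it. Unirradiated paraffin tumours run at the same core alongside the cases would make it estimable, at the price of further tissue and arrays.

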 - e. Primary and secondary breast cancer with any hormone status, including ER+, PR+/-, Her2neu-; ER+,PR+/-, Her2neu +; ER-,PR-, Her2neu-; ER-/PR-, Her2neu +

Exclusion criteria

- 1. Previously published research using gene expression data sets for primary breast cancers previously treated with chemotherapy, hormone therapy, or radiation prior to analysis will not be used for the control population
- 2. Previously published research using gene expression data from cell lines and animal studies will not be used for the control population
- 3. Non-epithelial breast malignancies, including lymphoma or sarcoma of the breast and melanoma and non-melanomatous skin cancers
- 4. In situ carcinomas of the breast

Materials/Data needed from the CCSS

- 1. Adequate secondary breast cancer tissue, from the study patients, to yield sufficient, amplifiable mRNA for eventual hybridization with the Affymetrix U133A Gene Chip.
 - a. N=54 (or more if possible)
 - b. At least five 10-micron scrolls (or equivalent quantity) of tumor tissue, verified by corresponding H&E slide, for each sample
- 2. Clinical data on study patients:
 - a. Age at childhood cancer diagnosis
 - b. Childhood primary tumor diagnosis
 - c. Childhood radiotherapy details (including total body irradiation and pelvic radiotherapy)
 - i. Dose and fractionation to irradiated site

- ii. Radiation dose to the chest
- iii. Age at start of radiation
- d. Age at breast cancer diagnosis
- e. Menopausal status at breast cancer diagnosis
- f. Age at death or last follow-up with current vital status for survival calculations
- g. Use of chemotherapy for treatment of the primary cancer

Statistical and Analytic Plans:

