To study our second aim, the molecular subtype status of the study population will be analyzed as a clinicopathologic factor for it's association with survival as well as with other factors such as age at childhood cancer diagnosis, type of childhood primary malignancy, age at time of radiation for childhood malignancy, radiation dose to the chest during childhood, total radiation dose received during childhood, use of chemotherapy for treatment of childhood malignancy, age and menopausal status at breast cancer diagnosis, and stage at breast cancer diagnosis. Correlative analysis (Spearman's rho, t-tests, ect.) will be used to test for univariable associations between the molecular subtype and the cross-sectional demographic variables. For the time-to-event outcomes such as survival and time to onset of breast cancer the log-rank test will be used to determine univariate associations of the molecular subtype (key risk factor of interest) with these outcomes intervals. Additional risk factors such as age at childhood cancer diagnosis, age at time of radiation for childhood malignancy, and radiation dose to the chest during childhood will also be evaluated similarly. Cox proportional hazards models will be used to evaluate multivariable associations between molecular subtype and each of the time-to-event outcomes, adjusting for other factors found to be significant in univariable analyses, or considered *a priori* to be important to include in the model (e.g. age at diagnosis, breast cancer stage, etc.)

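### The .cel comparison is said to reveal expression unique to irradiated breast tissue, but no unirradiated comparator is named, and against the published controls irradiation cannot be separated from tissue processing

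*Protocol*

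**What the plan says.** The first paragraph of Statistical and Analytic Plans describes the clustering on 249 genes, which "will be performed in an unsupervised manner on the 54 study and 1,619 control cases together". It provides for log-transformation and RMA normalisation of all cases, to deal with batch and paraffin effects. It also provides a quality check for genes sensitive to formalin fixation and paraffin, with exclusion from the final clustering.

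The second paragraph adds another step: "The raw data from the .cel files of the study population will also be compared". Its first purpose is to identify the genes that define a novel subclass, should the cases form their own cluster. Its second purpose is broader: "This approach will also allow the identification of gene expression, unique to previously radiated breast tissue, which spans across all subtypes".

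Inclusion criterion 1 defines the cases as "Survivors from the Childhood Cancer Survivor Study Cohort who subsequently developed breast cancer after thoracic radiation, with available breast tissue". The primary endpoint is "The patterns of gene expression and distribution of molecular subtypes of radiation induced breast cancer compared to spontaneous/primary breast cancer". The Figure 2 legend describes the 249-gene analysis as "applied to 1,619 cases from publicly available U133A-derived .cel files", so control array files are in hand.

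The data request to the CCSS (item 2c.ii) includes "Radiation dose to the chest". The paragraph on Specific Aim 2 opens with this plan: "the molecular subtype status of the study population will be analyzed as a clinicopathologic factor for it's association with survival as well as with other". Chest dose is on the list that completes the sentence. Chest dose is also evaluated against survival and time to onset of breast cancer.

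**The concern.** A claim that expression is unique to irradiated tissue needs a reference that was not irradiated. The sentence describing the comparison names only the study population. The preceding paragraph uses the word study for the 54 cases and control for the 1,619 published tumours. On that usage the comparison is among irradiated tumours only, and it would yield genes that vary between irradiated tumours.

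If the controls are meant, a different difficulty arises. The cases are paraffin-embedded samples hybridised at the study's own core facility, while the controls come from published datasets. A processing artefact that affects all cases alike would appear as a shift in every subtype, which is the same pattern that the protocol would read as a radiation signature.

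Expression pattern is part of the primary endpoint. The overriding hypothesis is that radiation leaves the molecular phenotype essentially unchanged, so a falsely reported radiation signature would count directly against it.

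**Working it through.** The protocol gives no figure for this step, so there is none to reproduce. The check is whether an irradiation effect can be estimated under each reading, followed by what a dose analysis within the cases could detect.

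**Inputs.** 54 study cases, all irradiated (inclusion criterion 1); 1,619 controls without previous cancer diagnosis or treatment (inclusion criterion 2). Total 54 + 1,619 = 1,673.

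**Estimability for any one gene.** Take the model: expression = intercept + irradiation effect + error.

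| Reading | Design columns | Rank | Consequence |
|---|---|---|---|
| Cases only (54) | intercept, irradiated | 1 of 2 | Irradiated equals 1 for everyone and duplicates the intercept, so there is no estimate |
| Cases and controls (1,673) | intercept, irradiated | 2 of 2 | A case-control difference can be estimated |
| Cases and controls, allowing for processing | intercept, irradiated, paraffin/batch | 2 of 3 | The last two columns are identical, so only their sum can be estimated |

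The third row assumes that no control shares the cases' processing. The protocol does not state how the control tissue was preserved or processed. If some controls did share it, the separation would be partial.

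**Do the stated safeguards reach this step?** Joint RMA normalisation aligns the arrays overall, but it cannot identify and remove a gene-specific offset that coincides with case status. The paraffin quality check could remove the worst affected genes, but the text applies its exclusions to the clustering and is silent about the second comparison.

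**Chest dose.** Set side by side, the data request collects it and the second-aim analysis relates it to subtype, survival and time to onset. Subtype is assigned from the 249-gene clustering, so dose is related to an expression-derived class. It is not related to expression gene by gene. A test of dose against subtype cannot reveal a change common to all subtypes.

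**What a dose analysis within the cases could detect.** For 80% power with n = 54 and no covariates, detectable r = tanh((z₁₋α/₂ + 0.8416)/√(n − 3)), with √51 = 7.141:

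- α = 0.05: tanh((1.960 + 0.842)/7.141) = 0.37
- α = 0.001: tanh((3.291 + 0.842)/7.141) = 0.52
- α = 0.0001: tanh((3.891 + 0.842)/7.141) = 0.58

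With five adjustment terms (assumed: four subtype indicators and age), √51 becomes √46 = 6.782, and the values rise to about 0.39, 0.54 and 0.60.

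**Subtype counts.** At the 50/20/20/10% expected under Specific Aim 1, 54 cases give 27, 10.8, 10.8 and 5.4, or about 27/11/11/5.

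**The case against.** The strongest reply is that the controls are the intended comparator. The primary endpoint is worded as a comparison with spontaneous cancer, the control array files are available, and the Figure 2 legend says that the case data will be analysed in the context of the control population. This stands as far as it goes. A reader might infer that the step carries no information about irradiation at all, but that follows only if the comparison is confined to the cases. With controls the contrast can be estimated; what it cannot do is attribute a difference to radiation rather than processing.

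A reader might also infer that chest dose is never related to expression. The documents do not support that, because dose is tested against molecular subtype, which is itself derived from expression. Only the gene-level analysis is absent. No aim or endpoint promises one, so its absence is a missed opportunity and not an error.

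A third tempting inference is that raw means un-normalised intensities. The phrase may equally mean starting from the full array files and not only the 249-gene subset, which fits the purpose of finding genes for a new subclass. Nothing says that normalisation is skipped.

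Finally, a dose analysis would not itself supply an unirradiated reference. That is correct, and it is why the dose analysis should be an addition and not a replacement. Replacing the step would also lose the identification of novel-subclass genes.

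None of this rescues the uniqueness claim, which the protocol makes explicitly and which fails on either reading.

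**Conclusion.** The concern holds in a limited form. The protocol draws an inference, expression unique to irradiated tissue across all subtypes, that the described comparison cannot support. Among the cases alone an irradiation effect cannot be estimated. Against the controls it can be estimated but is fully confounded with paraffin processing and batch, on the assumption that no control shares the cases' processing. The protocol recognises paraffin and batch effects for the clustering but does not carry the gene exclusions over to this step.

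The point does not show that the comparison is worthless. It remains usable for describing a novel subclass and, with controls, for describing differences whose cause is left open. The size of any processing artefact cannot be worked out from the document. What can be said is that the design gives no means of telling it from a radiation effect. The matter deserves correction because expression pattern is part of the primary endpoint and the correction is cheap.

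**What to change.** 1. Keep the second .cel comparison for identifying the genes of any novel subclass.
2. State that its comparator is the 1,619 controls, that it uses RMA-normalised data, and that genes found sensitive to paraffin processing are excluded here as well as from the clustering.
3. Replace the claim of expression unique to irradiated tissue with a description of expression that differs between cases and controls and cannot be separated from processing.
4. Add, labelled exploratory, a regression within the cases of normalised expression on continuous chest dose, adjusted for subtype and age at breast cancer diagnosis, with false-discovery-rate control. Use age at radiation, childhood diagnosis and chemotherapy as sensitivity adjustments. Do not make the result depend on slopes agreeing in sign across subtypes that reach a minimum count such as 10: with about 27/11/11/5 cases expected, two subtypes sit at that threshold and one falls below it.

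The cost is a text change and analysis time, since chest dose is already requested. The dose analysis has low power, so only strong associations would be found, and fewer still if chest doses fall in a narrow range. It would miss any radiation effect that does not vary with dose.
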